*Expected attrition in each of the lead groups is based on the rationale provided above the table as well as larger attrition expected in older leads.

[figure not shown]
At enrollment, medical history, demographic data and lead measurement data will be collected. Additionally, cinefluoroscopy (AP, LAO 45° or the best possible LAO view, RAO 45° or the best possible RAO view) will be performed to determine the prevalence of lead compromise. A copy of

cinefluoroscopy performed as part of separate screening can be used to determine the prevalence of lead compromise as long as all three views (AP, LAO 45° or the best possible LAO view, RAO 45° or the best possible RAO view) are available. In patients with evidence of externalized conductors or other visual lead anomalies (fracture, subclavian crush, kink, broken filars on a shocking coil and other irregularities) the following chest x-rays or other available imaging studies will be collected (if available): a) earliest imaging study showing evidence of externalized conductors or other visual lead anomaly and b) latest imaging study that does not show any evidence of externalized conductors or other visual lead anomaly

Data will be collected at 6, 12, 18, 24, 30, and 36 months post enrollment and during any unscheduled follow-up visits due to patient symptoms suggestive of or with evidence of lead electrical problems. Additionally, cinefluoroscopy (AP, LAO 45° or the best possible LAO view, RAO 45° or the best possible RAO view) will be performed in all patients to determine the incidence and mechanical progression of externalized conductors at the 12, 24, and 36 month visits.

During any follow-up visits, device data and stored electrograms will be collected. All clinical events such as hospitalizations, emergency room visits, and adverse events will also be collected. All study data, including device data and stored electrograms will be sent to SJM electronically. If any lead being followed in this study develops a significant electrical abnormality suggestive of lead malfunction and x-ray or cinefluoroscopy would be performed as per the site standard of care then copies of x-ray or cinefluoroscopy should be submitted to SJM.

During the course of the study, any explanted leads should be returned to Returned Goods, St Jude Medical, Sylmar, CA, for analysis.

Study Flow Diagram

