3.2 Study Outcome Measures

3.2.1 Primary Outcome Measures

3.2.1.1 The prevalence of electrical dysfunction in the Riata, Riata ST, QuickSite/QuickFlex (1056T, 1058T, 1156T, 1158) and Durata leads.

Lead Population

All enrolled leads within the Riata, Riata ST, QuickSite/QuickFlex (1056T, 1058T, 1156T, 1158) and Durata lead groups.

Analysis:

The prevalence of electrical dysfunction will be calculated as the number of leads that have electrical dysfunction at the time of enrollment in each of the 4 lead groups divided by total number of leads in enrolled patients in each of the 4 lead groups. The one-sided 95% UCB for prevalence will be calculated using Clopper-Pearson exact method.

3.2.1.2 The prevalence of externalized conductors in the Riata, Riata ST, QuickSite/QuickFlex (1056T, 1058T, 1156T, 1158) and Durata leads.

Lead Population

All enrolled leads within the Riata, Riata ST, QuickSite/QuickFlex (1056T, 1058T, 1156T, 1158) and Durata lead groups.

Analysis:

The prevalence of externalized conductors will be calculated as the number of leads that have been shown to have externalized conductors by imaging at the time of enrollment in each of the 4 lead groups divided by total number of leads in enrolled patients in each of the 4 lead groups. The one-sided 95% UCB for prevalence will be calculated using Clopper-Pearson exact method.

3.2.1.3 The prevalence of other visual lead anomalies by each subcategory (fracture, kink, subclavian crush, other irregularities) in the Riata, Riata ST, QuickSite/QuickFlex (1056T, 1058T, 1156T, 1158) and Durata leads.

Lead Population

All enrolled leads within the Riata, Riata ST, QuickSite/QuickFlex (1056T, 1058T, 1156T, 1158) and Durata lead groups.

Analysis:

The prevalence of other visual lead anomalies (by each subcategory) will be calculated as the number of leads that have been shown to have other visual anomaly (by each subcategory) at the time of enrollment in each of the 4 lead groups divided by total number of leads in enrolled patients in each of the 4 lead groups. The one-sided 95% UCB for prevalence will be calculated using Clopper-Pearson exact method.

3.2.1.4 The annual hazard rate of lead electrical dysfunction (from enrollment) by lead subgroups in the Riata, Riata ST, QuickSite/QuickFlex (1056T, 1058T, 1156T, 1158) and Durata leads.

Lead Population

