All enrolled leads being followed in this study within the Riata, Riata ST, QuickSite/QuickFlex (1056T, 1058T, 1156T, 1158) and Durata lead groups.

Analysis:

The annual hazard rate will be assessed separately in each of the 4 lead groups along with the subgroups listed in Table 2.

For QuickSite/QuickFlex leads only, data from patients with an additional 1 year of follow-up will contribute to 2 separate lead subgroups (See Section 3.4.5).

3.2.1.5 The annual hazard rate of new cases of externalized conductors (from enrollment), by lead subgroups in the Riata, Riata ST, QuickSite/QuickFlex (1056T, 1058T, 1156T, 1158) and Durata leads.

Lead Population

All enrolled leads being followed in this study within the Riata, Riata ST, QuickSite/QuickFlex (1056T, 1058T, 1156T, 1158) and Durata lead groups.

Analysis:

The annual hazard rate will be assessed separately in each of the 4 lead groups along with the subgroups listed in Table 2.

For QuickSite/QuickFlex leads only, data from patients with an additional 1 year of follow-up will contribute to 2 separate lead subgroups (See Section 3.4.5).

3.2.1.6 The annual hazard rate of new cases of other visual lead anomalies by each subcategory (from enrollment), by lead subgroups in the Riata, Riata ST, QuickSite/QuickFlex (1056T, 1058T, 1156T, 1158) and Durata leads.**Lead Population**

All enrolled leads being followed in this study within the Riata, Riata ST, QuickSite/QuickFlex (1056T, 1058T, 1156T, 1158) and Durata lead groups.

Analysis:

The annual hazard rate will be assessed separately in each of the 4 lead groups along with the subgroups listed in Table 2.

For QuickSite/QuickFlex leads only, data from patients with an additional 1 year of follow-up will contribute to 2 separate lead subgroups (See Section 3.4.5).

3.2.1.7 Prevalence of “other insulation anomalies” in “returned leads” (as defined in section 2.0), by lead subgroups in the Riata, Riata ST, QuickSite/QuickFlex (1056T, 1058T, 1156T, 1158) and Durata leads.**Lead Population**

Any enrolled lead in the study that gets returned to St. Jude Medical for analysis.

Analysis:

The prevalence of “other insulation anomalies” will be calculated as the number of returned leads that have “other insulation anomalies” in each of the 4 lead groups divided by the total number of returned leads in enrolled patients in each of the 4 lead groups. The one-sided 95% UCB for prevalence will be calculated using Clopper-Pearson exact method.

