3.4 Study Procedures

Study procedures are described in the sections below. Refer to Table 3 for an overview of the required study procedures. St. Jude Medical will provide supplemental step by step instructions for obtaining required study data.

Table 3: Study Procedures

	Enrollment	6, 18, and 30 month visit	12, 24, and 36 month visit	Unscheduled visit	Extended 42 month visit ^c	Extended 48 month visit ^c
Informed Consent	✓					
Demographics	✓					
Medical History	✓					
Electrical Malfunction History	✓					
Cinefluoroscopy (AP, LAO 45° or the best possible LAO view, RAO 45° or the best possible RAO view)	✓ ^a		✓			✓ ^c
Chest X-ray or Any Imaging Study	✓ ^b					
Lead Measurements	✓	✓	✓	✓	✓ ^c	✓ ^c

a - Patients who underwent cinefluoroscopy at enrollment as part of the “Riata Lead Evaluation Study” will not be required to undergo another baseline cinefluoroscopy.

b - In patients with evidence of externalized conductors under cinefluoroscopy at enrollment, the following chest x-ray or imaging study will be collected, if available: a) earliest chest x-ray or imaging study with evidence of externalized conductors and b) latest chest x-ray or imaging study with no evidence of externalized conductors.

c - *For only eligible patients with QuickSite/QuickFlex leads that consent for an additional year of follow-up (42 and 48 Month Visits).*

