3.4.1 Enrollment

Upon determination of study eligibility, informed consent will be obtained from eligible patients by the principal investigator or designee prior to initiation of any study related screening activities.

Patients with Riata, Riata ST, QuickSite (1056T or 1058T), QuickFlex (1156T or 1158T), and Durata leads with model numbers and lead implant dates indicated in Table 1 will be screened for evidence of externalized conductors or other visual lead anomalies through cinefluoroscopy that will include three videos/cines of the entire lead length as well as the pocket area (AP, LAO 45° or best possible LAO, RAO 45° or best possible RAO). A copy of Cinefluoroscopy performed as part of separate screening can be used to determine the incidence of externalization as long as all three views (AP, LAO 45° or the best possible LAO view, RAO 45° or the best possible RAO view) are available. Patients who underwent cinefluoroscopy at enrollment as part of the “Riata Lead Evaluation Study” will not be required undergo another baseline cinefluoroscopy. In patients with evidence of externalized conductors, the following chest x-rays will be collected, if available: a) earliest chest x-ray or imaging study showing an evidence of externalized conductors or other visual lead anomalies and b) latest chest x-ray or imaging study that does not show any evidence of externalized conductors or other visual lead anomalies.

Data will be collected on the patient demographics (gender, age, medical history, history of electrical dysfunctions in the past, etc). Lead electrical performance will also be evaluated.

For the purposes of this study, a patient is considered enrolled upon signing of the consent form and collection of data at enrollment visit. Data previously collected from patients enrolled in other ongoing SJM registries may be used for this study.

Data to be captured at enrollment includes:

- RV lead capture threshold, lead pacing impedance and signal amplitude (only required if RV lead model and implant date is listed in Table 1)*
- LV lead capture threshold, lead pacing impedance in a bipolar configuration (only required if LV lead model and implant date is listed in Table 1)
- High Voltage Lead impedance (HVLI) testing – mandatory for Current/ Promote or later ICD and CRT-D, optional for devices before Current/Promote ICD and CRT-D, and not applicable to CRT-P

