3.4.2 Follow-up Requirements

The schedule of follow-up visits is based on the date of enrollment. Table 4 outlines the time window that is permitted for each of the study interval visits.

Table 4: Study Interval Time Windows

Visit Type	6*, 12, 18, 24, 30, and 36 months	42** and 48** Months
Window	± 60 days*	± 60 days**

*In order to accommodate many patients with Riata/Riata ST silicone leads who were previously enrolled in the “Riata Lead Evaluation Study” in last 10 months, the window for the 6 month visit will be -60 days to + 120 days.

**For only those eligible QuickSite/Quickflex patients that consent to extended follow-up.

Cinefluoroscopy (AP, LAO 45° or the best possible LAO view, RAO 45° or the best possible RAO view) will be taken to determine the incidence/ mechanical progression of externalized conductors at the 12, 24, and 36 month visits for all patients and at the 48 month visit for only those eligible QuickSite/QuickFlex patients that consent for extended follow-up.

If the Riata, Riata ST, QuickSite (1056T/1058T), QuickFlex (1156T/1158T), or Durata lead develops a significant electrical abnormality suggestive of lead malfunction and x-ray or cinefluoroscopy would be performed as per the site's standard of care. The x-ray or cinefluoroscopy should be submitted to SJM.

All patients will be required to attend the in-clinic follow-up visits at 6, 12, 18, 24, 30, and 36 months. Only those eligible QuickSite/QuickFlex patients that consent for extended follow-up will be required to attend the 42 month in-clinic follow-up visit. Data to be captured includes the following:

- RV lead capture threshold, lead pacing impedance and signal amplitude (only required if RV lead model and implant date is listed in Table 1) *
- LV lead capture threshold, lead pacing impedance in a bipolar configuration (only required if LV lead model and implant date is listed in Table 1)
- High Voltage Lead impedance (HVLI) testing – mandatory for Current/ Promote or later ICD and CRT-D, optional for devices before Current/Promote ICD and CRT-D, and not applicable to CRT-P

*** Note:** If patient is pacer dependent or R-wave is not available then RV signal amplitude is not required.

Upon completion of the follow-up above visits, complete the applicable CRFs using the EDC system and submit the supportive data listed below to St. Jude Medical.

- Follow-up CRF
- Product Out of service (if applicable)
- Electronic device session records

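### Outside the rollover patients, a screening cine of any age may serve as the imaging baseline while prevalence and incidence are dated from enrollment, so onsets in the gap are counted as new cases

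*Combined protocol and SAP*

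**What the plan says.** **Baseline image.** Section 3.1 calls for three-view cinefluoroscopy at enrollment but allows a substitute: "cinefluoroscopy performed as part of separate screening can be used to determine the prevalence of lead compromise as long as all three views" are available. Section 3.4.1 repeats the allowance with a different purpose: "A copy of Cinefluoroscopy performed as part of separate screening can be used to determine the incidence of externalization as long as all three views" are available. One section ties the reused cine to prevalence and the other to incidence. Neither sets a maximum interval before enrollment.

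**Rollover patients.** They have a separate exemption in Table 3, note a: "Patients who underwent cinefluoroscopy at enrollment as part of the “Riata Lead Evaluation Study” will not be required to undergo another baseline cinefluoroscopy".

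**Dating of the outcomes.** Section 3.2.1.2 counts "the number of leads that have been shown to have externalized conductors by imaging at the time of enrollment". Section 3.2.1.5 is headed "The annual hazard rate of new cases of externalized conductors (from enrollment" (cut here before its closing bracket). Section 3.2.2.1 starts the Kaplan-Meier clock at enrollment, in leads free of the finding at that point. Sections 3.2.1.3, 3.2.1.6 and 3.2.2.2 do the same for other visual anomalies. Section 3.4.1 defines enrollment as signed consent plus data collection at the enrollment visit, so it is not tied to the date of the cine. The next scheduled cine is at 12 months.

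**The concern.** With a reused cine, the lead's status is known on one date and its clock starts on a later one. Suppose a lead is negative on the old cine and externalizes before enrollment. It enters as free of the finding, is absent from the prevalence numerator, and is first seen as positive at the 12-month cine. It then counts as incident, although the interval in which the event occurred is not in the denominator.

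The direction of the error is fixed: prevalence down, early incidence up. Prevalence and annual hazard of externalized conductors and of other visual anomalies are all primary outcomes. The study exists to separate what is already present from what develops later, and the error moves cases from the first to the second.

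**Working it through.** **Stated figure.** The plan gives no figure on this point, so there is none to reproduce. The check compares the rules and then sizes the effect under assumptions.

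**Does anything else correct the gap?**
- Table 4 gives follow-up visits a window of 60 days either side. The baseline cine has no window.
- Central reading (11.2) standardizes interpretation, not timing.
- Older images are sought only for leads that already show a finding, and only if available (3.1, 3.4.1). They cannot update an old negative.
- No section moves time zero to the cine, treats onset as interval-censored, or plans an analysis by cine age.
- Section 3.2.2.4 starts its clock at the date of detection. An imaging-date origin is thus already used in the plan, but not for incidence.

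**Who is affected?** For rollover patients, 3.4.2 states that "the window for the 6 month visit will be -60 days to + 120 days", to accommodate patients enrolled up to 10 months before. Six months plus 120 days is about 10 months. This suggests that their clock runs from enrollment in the earlier study, when their cine was taken, so they probably have no gap. The protocol does not say so outright. The second QuickSite/QuickFlex cohort (Table 5) takes a scheduled 12-month visit as its baseline, so it adds no gap of its own.

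**Size.** Assumed inputs, none given in the documents: constant hazard h of 1%, 3% or 6% per year; gap g of 3, 6 or 12 months (0.25, 0.5 or 1 year); share f of leads with a reused cine of 100% or 25%. All leads considered are negative on the baseline cine.

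- True year-1 risk: 1 − exp(−h)
- Apparent year-1 risk: f[1 − exp(−h(1+g))] + (1−f)[1 − exp(−h)]
- 3-year risk: the same with 3 in place of 1
- Prevalence missed among cine-negative leads: f[1 − exp(−hg)]

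Example with h = 0.03, g = 0.5, f = 1: apparent 1 − exp(−0.045) = 4.40%; true 1 − exp(−0.03) = 2.96%; ratio 1.49. Prevalence missed is 1 − exp(−0.015) = 1.49 percentage points.

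Reused-cine leads only (f = 1):

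| Quantity | h | No gap | 3 months | 6 months | 12 months |
|---|---|---|---|---|---|
| Year-1 risk | 1% | 1.00% | 1.24% | 1.49% | 1.98% |
| | 3% | 2.96% | 3.68% | 4.40% | 5.82% |
| | 6% | 5.82% | 7.23% | 8.61% | 11.31% |
| Year-1 ratio | 1–6% | 1 | 1.24–1.25 | 1.48–1.50 | 1.94–1.99 |
| 3-year ratio | 1–6% | 1 | 1.08 | 1.15–1.16 | 1.30–1.33 |
| Prevalence missed (points) | 1–6% | 0 | 0.25–1.49 | 0.50–2.96 | 1.00–5.82 |

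Whole group if 25% of leads reuse a cine (f = 0.25): year-1 ratios of about 1.06, 1.12 and 1.24. At h = 3% the apparent year-1 risks are 3.14%, 3.32% and 3.67% against 2.96%.

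With g = 0, or with time at risk counted from the cine, the bias from the gap is zero by construction.

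**The case against.** **Reuse is an exception of unknown size.** Section 3.1 and Table 3 make an enrollment cine the norm, and section 10.0 expects at least four procedures, which fits enrollment plus 12, 24 and 36 months. If reused cines are few or recent, the error is negligible. This stands, and the size must stay conditional. It does not remove the point, because the rule as written admits a cine of any age and then dates the result from enrollment.

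**Much of the Riata population probably has no gap.** The timeline in 3.1.1 shows 720 eligible enrollments when the initial protocol (Rev F) was approved. The combined Riata and Riata ST target in Table 2 is 925 (195+185+180+185+180). If most of the 720 are rollover patients, the groups of greatest interest are largely unaffected. This stands and is why the point is limited to other leads.

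**Starting the clock at the cine could add survivorship bias,** because a lead must stay in service from cine to enrollment to be enrolled. This stands in part. The interval is truly at risk for an onset first seen on a later cine. What remains concerns only leads lost before enrollment, and it is minor.

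**A reader might also infer that sites chose patients on known screening results.** Consent need precede only study-related screening, and section 3.3 has no consecutive-enrollment rule, whereas 3.4.5 requires every eligible patient to be approached for extended follow-up. That leaves selection possible. No document shows that it happened, and its direction would be unknown.

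**Conclusion.** The point holds for imaging endpoints in leads outside the rollover that use a separate-screening cine. Followed as written, the plan understates their prevalence and overstates their early incidence. This follows from stated rules and is more than a missing detail.

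The inflation in year 1 is about 1.25, 1.5 and 1.95 times for gaps of 3, 6 and 12 months among reused-cine leads. It fades to about 1.08, 1.15 and 1.3 times over three years, and it is diluted in proportion to the share of leads affected. These figures rest on a constant hazard of 1% to 6% per year and on assumed gaps and shares.

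Three stronger readings are not supported. Not every pre-enrollment onset is miscounted: one visible on the reused cine is counted as prevalent. The group-level primary results need not be off by the reused-cine ratios, since the share of such leads is not given. Electrical dysfunction is adjudicated from device records and is not affected.

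**What to change.** For imaging endpoints only:

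1. Record the baseline cine date and whether the cine was reused or taken after consent.
2. Start time at risk at the baseline cine, or treat onset as interval-censored between the last negative and first positive cine.
3. State that imaging prevalence is as of the cine date.
4. Add a sensitivity analysis of imaging prevalence and incidence that excludes reused cines taken more than 60 days before enrollment, borrowing the limit from Table 4.
5. Report prevalence by cine source. This is a descriptive check on selection and cannot settle it, since it does not show whether the site knew the result.
6. State that the rollover clock starts at enrollment in the earlier study, if that is the intention, and reconcile 3.1 with 3.4.1 on whether a reused cine serves prevalence or incidence.

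Keep subgroup assignment by lead age at enrollment, as in Table 2. Re-dating lead age for imaging alone could put one lead in different subgroups for different endpoints.

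**Cost.** Extra analysis rows and one date to capture. The cine is submitted to the sponsor at enrollment (3.4.1), but the documents do not say that its date is recorded. The minor survivorship issue remains. No new patients, visits or imaging are needed.

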3.1.1 Projected Study Timeline

A projected timeline for the SJM Cardiac Lead Assessment Study is provided below. Since patients implanted with Riata and Riata ST silicone leads enrolled in the Riata Lead Evaluation Study will be rolled over to this protocol, the timeline takes into the account the initiation of the Riata Lead Evaluation Study done in the 4th quarter of 2011; dates will change based on the date enrollment begins again, and/or the actual enrollment rate.

Time = 0; month 1 September 2011	Time = month 2	Time = month 3	Time = month 4 December 2011	Time = month 5	Time = month 6 February 2012	Time = month 7	Time = month 8	Time = month 9	Time = month 10 June 2012	Time = month 11	Time = month 12 August 2012
Study Initiation			4 site with IRB approval	9 sites with IRB approval	11 sites with IRB approval	17 sites with IRB approval	22 sites with IRB approval	24 sites with IRB approval	24 sites with IRB approval	Enrollment Closed for Riata Silicone Leads	Received FDA 522 Order
			Enrollment = 5	Enrollment = 36	Enrollment = 72	Enrollment = 216	Enrollment = 329	Enrollment = 77	Enrollment = 47		
		Cumulative enrollment	5	41	113	329	658	735	782	Patient follow-up	-----
Time = month 13 September 2012					Time = FDA approval of initial Protocol Rev F February 2013	Time = FDA approval + 1 month	Time = FDA approval + 2 months	Time = FDA approval + 3 months	Time = FDA approval + 4 months	Time = FDA approval + 5 months	Time = FDA approval + 6 months
Protocol Submitted to FDA based on 522 order	//	//	//	//			Enrollments for 522 Order Eligible Leads				29 sites with IRB approval
	//	//	//	//	522 Order eligible enrollments= 720	Enrollment = 4	Enrollment = 56	Enrollment = 66	Enrollment = 77	Enrollment = 126	Enrollment = 128
Patient follow-up	-----	-----	-----	-----	-----	Cumulative enrollment= 724	780	846	923	1049	1177
Time = FDA approval + 7 months	Time = FDA approval + 8 months	Time = FDA approval + 9 months	Time = FDA approval + 10 months	Time = FDA approval + 11 months	Time = FDA approval + 12 months Feb. 2014	-----	Time = FDA approval + 18 months	-----	Time = FDA approval + 24 months Feb. 2015	-----	-----
Enrollment = 168	Enrollment = 80	Enrollment = 58	Enrollment = 36	Enrollment = 16	35 sites with IRB approval Enrollment = 77		43 sites with IRB approval Enrollment = 217		44 sites with IRB approval Enrollment = 135		
Cumulative enrollment = 1345	1425	1483	1519	1535	1612		1829		1964		
Time = Orig. FDA approval + 32 months October 2015 Anticipate FDA approval of protocol revision K	-----	Time = Orig. FDA approval + 37 months Durata and Riata enrollment completed	-----	Time = Orig. FDA approval + 42 months QuickSite/QuickFlex enrollment completed	-----	-----	Time = Orig. FDA approval + 78 months	Time = Orig. FDA approval + 79 months	Time = Orig. FDA approval + 80 months	Time = Orig. FDA approval + 81 months	Time = Orig. FDA approval + 82 months
		55 sites with IRB approval		Patient follow-up	//	//	Follow-up completed		Complete Monitoring	Data Analysis	Final report submission
Projected Cumulative enrollment = 2025		2060		2110							

